3.1.4.3 Whole breath analysis

Human tidally exhaled air contains contributions of about 150 ml of dead space and 350 ml of alveolar respiration. Exhaled breath contains more than 3,500 identified and many more unidentified components. Most of exhaled breath volume is constituted by gases like O₂, NO, and CO₂. Additionally, there is a large number of VOCs, present in minute quantities whose analysis by GC-MS was pioneered by Linus Pauling's group in the 1970ies [50,51].

Real-time analysis of so-called breathprints (exhalome) via MS is a highly promising but little explored area of translational research. Rather than comparing only small numbers of pre-selected or highly salient compounds, breathprints represent relative intensity patterns (so-called mass-to-charge or m/z pairs) for a multitude compounds reflecting subject-specific metabolic signatures. Potential future applications include internal body clock estimation, disease risk prediction and monitoring of treatment adherence [52]. Secondary electrospray ionisation-mass spectrometry (SESI-MS) has been developed for that purpose [53]. It can detect differences between individual breathprints that are reasonably stable over time and follow predictable diurnal patterns [54,55]. SESI-MS' simple non-invasive set-up merely requires persons to exhale through a sterile plastic mouthpiece into a heated tube making it highly appealing as a clinical tool. So far, SESI-MS breathprint analysis has not been applied to children with respiratory complaints.

Our study will be one of the first to analyse whole breath molecular composition rather than investigate isolated gases or molecules. In contrast to previous studies, this unbiased approach enables the identification of disease-specific breath patterns including thousands of volatile compounds. Our method allows for the simultaneous analysis of tiny concentrations of molecules, many of which have hitherto not yet been molecularly characterised.

3.1.4.4 Recent finding on breath analysis in children with respiratory diseases

Recently, the use of mass spectrometry in breath analysis in respiratory disease gained more attention due to major technical advances. In a case-control study in 120 Dutch children exhaled breath was analysed by gas chromatography coupled with Mass Spectrometry (GC-MS). Breath analysis could accurately distinguish children with asthma from healthy children, achieving a sensitivity of 89% and a specificity of 95% [56]. Two authors from a Dutch research group recently published prospective data from the ADEM (Asthma DEtection and Monitoring) cohort, where preschool children were followed from three to six years of age and breath profiles were repeatedly measured by GC-MS [57,58]. With a set of volatile organic compounds (VOCs) the population could be classified into healthy, transient wheezing and asthmatic with reasonable accuracy.

Until now no studies in children with PBB and/or chronic cough have been conducted. However, there are a small number of studies in cystic fibrosis (CF), a inherited lung dieseases that is characterized with chronic microbial infection and thereby resembling PBB. Robroeks et al. compared 48 CF and 57 control subjects who exhaled into plastic bags [59]. Breath-borne particles were immobilised before GC-MS analysis. Different breathing manoeuvres did not alter VOC patterns which reliably predicted CF status and Pseudomonas colonisation. Barker et al. followed a similar approach to study selected VOCs in 20 CF patients and 20 healthy controls [60]. They found good intra-subject reproducibility and associations with airflow limitation and Pseudomonas status.

A 2012 review of breath analysis in CF summarises its ability of identifying microbial airway colonisation, differentiation of CF from asthma and healthy controls, identification of steroid-naïve vs. steroid-treated CF patients and recognition of stable vs. acutely exacerbated CF patients [61]. However, all the earlier breath analysis data have to be interpreted in the light of several limitations. As breath was analysed by gas chromatography and real-time (as in SESI-MS), breath was collected and storaged in inert bags. Moreover, this technique requires sample pre-processing is necessary before analysis and issues like sample contamination and molecule degradation due storage and pre-processing are critical issues. SESI-MS not only circumvents these issues by real-time measurement, but also detects molecules with high sensitivity in a larger range than other mass spectrometry techniques [76, 77, 78].

3.2 Rationale for the research project

Preliminary results from the Zurich-based collaboration between the University Hospital of Zurich and the Eidgenoessische Technische Hochschule Zürich (ETHZ) have demonstrated the validity and reliability of SESI-MS in evaluating individuals' exhaled breathprints [52,55]. Feasibility studies are ongoing that clearly show that the technique is applicable in infants and preschool children. There is ample evidence that exhaled breath composition differs between healthy controls and children with respiratory disease and may be useful for non-invasive biomarker analysis.

The main objective is to provide evidence for the discriminative capacity of breath analysis by SESI-MS in children with respiratory symptoms and to translate the non-invasive, risk-free technique of breath

analysis into routine clinical practice. Due to limited objective measurements available for preschool children proper diagnosis of chronic respiratory disease is very challenging in this age range. This has important implications on disease morbidity and outcome as treatment and preventive measures depend on the correct diagnosis. To date many children are treated with repeated or long-term inhaled corticosteroids with minimal effect as do not suffer from asthma. On the other hand, children with asthma are not treated sufficiently to prevent long term sequela. Better phenotyping of children with chronic respiratory complaints allows correct and efficient therapy and will lead to personalized treatment approaches reducing side effects, improve efficacy and reduce disease burden and health costs. We aim to apply the methodology of SESI-MS to characterize early and non-invasively airway inflammation and metabolic processes due to airway inflammation.

Our research hypotheses are:

- The development of asthma later in life can be predicted by specific breath prints and/or specific molecules in exhaled breath in preschool children with chronic respiratory symptoms
- The diagnosis of protracted bacterial bronchitis can be preponed by breath analysis in preschoolers with chronic cough
- Breath analysis is capable to classify school-aged children with and without asthma (breath prints and/or specific molecules in exhaled breath)
- Specific breath prints predictive for asthma in school age can also be found in preschool children that are likely to develop asthma later in life
- Controlled and uncontrolled asthma can be distinguished by breath analysis in school-aged children
- Phenotyping of asthma based on specific breathprints is possible in school age children

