Background and Rationale:	Visits for respiratory disease account for 10% of pediatric emergency department visits and 20% of all paediatric hospital admissions. Major respiratory symptoms of respiratory diseases in childhood are wheezing and cough. Both are characteristics of acute and chronic airway diseases, which develop frequently in childhood. Wheezing is the clinical hallmark of obstructive lower airway diseases like asthma, "wheezy" bronchitis or bronchiolitis. Cough is a major characteristic of virtual all lower respiratory infections and may also be the sole presenting symptom of asthma. Whereas most of the children overcome acute episodes of respiratory symptoms without further sequelae, some are at increased risk to develop chronic airway disease. In particular recurrent wheezing in preschoolers has been clearly shown to be a predictor of asthma in school-age and prediction of asthma can be improved when taking chronic cough into account. However, prolonged bacterial airway infection (protracted bacterial bronchitis, PBB) is also characterized by chronic cough and is frequently misdiagnosed as asthma in particular in preschool age. This is manly to the limited objective measurements available in this age range and therefore diagnosis of chronic respiratory disease in preschool children is still challenging. Preliminary results from the Zurich-based collaboration between the University Hospital of Zurich and the Eidgenoessische Technische Hochschule Zürich (ETHZ) have demonstrated the validity and reliability of SESI-MS in evaluating individuals' exhaled breathprints. Feasibility studies are on-going and clearly show that the technique is applicable in infants and preschool children. There is ample evidence that exhaled breath composition differs between healthy controls and children with respiratory disease and may be useful for non-invasive biomarker analysis.						
Objective(s):	The main objective is to provide evidence for the effectiveness of breath anlaysis by SESI-MS in children with respiratory symptoms and to translate the non-invasive, risk-free technique of breath analysis into routine clinical practice.						
Outcome: Primary Outcome Secondary Outcome	Primary: Molecular composition of exhaled breath analysed by mass spectrometry Secondary: Other measurements: clinical record data, including lung function, allergic sensitization, venous blood markers, throat swab, radiological exams						

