3.1.4.2 Isolated Gaseous Components

Of all exhaled biomarkers, fraction of exhaled nitric oxide (FeNO) is the most studied biomarker and is the only exhaled biomarker with widespread clinical use. FeNO is considered to be a non-invasive marker of eosinophilic airway inflammation [42]. Whilst a standardized, online FeNO sampling technique is used in schoolchildren, unstandardized and offline FeNO sampling is mostly applied in preschool children [43]. We could previously show that FeNO levels were higher in wheezing preschool children with probable asthma compared to preschool children without symptoms or with probable transient wheezing symptoms [44]. However, the study had a cross-sectional design and used 'probable asthma' as a diagnosis. In a longitudinal cohort, it was found that a FeNO concentration of ≥ 30 ppb at preschool age could predict persistence of wheezing symptoms at three years (sensitivity 77%, specificity 94%) [45]. Accordingly, we could demonstrate in a prospective cohort study with 391 preschool children (aged three months to four years) that FeNO was elevated in preschool children who developed asthma at school age compared to children without later asthma [46]. In the PIAMA study, it was demonstrated that FeNO and IgE (but not airway resistance) measured at four years of age were predictive for asthma symptoms at age eight, independent of clinical his- tory [47]. In a subsequent analysis of this cohort, FeNO was related to the classic wheezing phenotypes with increased levels in persistent wheezing compared to transient wheezing phenotypes [12,48]. However, elevated FeNO in persistent wheezers was only present in children with allergic sensitization [49]. As presence of atopy seems to modify the relationship between FeNO and wheezing phenotypes, a different pathophysiology of wheeze in atopic and non-atopic children might be present. Potentially, eosinophilic inflammation might play a predominant role in atopic persistent wheezers, whilst other types of inflammation such as neutrophilic inflammation might play an important role in non-atopic persistent wheeze. As FeNO compromises only one (eosinophilic) biomarker, it might not be sufficient to study the broad range of preschool wheezers, and additional biomarkers are needed to be studied.

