4. OBJECTIVES, ENPOINTS/OUTCOMES AND OTHER STUDY VARIABLES

4.1 Objectives

(STROBE 3) [6]

Zürich Exhalomics is a flagship project of the Universities of Zürich (University of Zürich and ETHZ) and the department of paediatric pneumology of the University Children's Hospital Zürich is part of this interdisciplinary consortium. We plan a clinical study to investigate specific breath prints and molecules for the assessment and prediction of children with chronic respiratory symptoms by breath analyses with SESI-MS.

We plan to reach this aim by answering following research questions:

- Do breath prints separate healthy preschool children differ from their peers with respiratory symptoms? (WP I, see below)
- Do breath profiles differ among symptomatic preschool children? (WP I)
- Is there an association between breath profiles and conventional clinical phenotypes? (WP I)
- Is breath analysis by SESI-MS in preschool age diagnostic for PBB? (WP I)
- Do the breath profiles in preschool age predict outcomes later in life (asthma, transient wheeze)? (WP I & II)
- Do breath prints differ between healthy school-aged children differ and their asthmatic peers diagnosed by conventional methods (clinics, lung function, allergy testing)? (WP III)
- Can SESI-MS distinguish between controlled and uncontrolled asthma? (WP III)
- Can phenotyping by SESI-MS in school-age children be replicated in a second population? (WP II & III)
- Which single biomarkers for distinct respiratory diseases can be extracted from breath profiles from preschool and school-aged children? What is their role in disease pathogenesis? (WP I, II & III)
- How can SESI-MS analysis be streamlined for routine clinical use? (WP I, II & III)
- Are breathprints associated with microbial colonisation, symptoms, and clinical history? (WP I, II & III)

Our research hypotheses are:

- The development of asthma later in life can be predicted by specific breath prints and/or specific molecules in exhaled breath in preschool children with chronic respiratory symptoms
- The diagnosis of protracted bacterial bronchitis can be preponed by breath analysis in preschoolers with chronic cough
- Breath analysis is capable to classify school-aged children with and without asthma (breath prints and/or specific molecules in exhaled breath)
- Specific breath prints predictive for asthma in school age can also be found in preschool children that are likely to develop asthma later in life

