7.3 Planned analysis

(STROBE 12a-d) [6]

Demographic and clinical characteristics will be compared using independent-sample pairwise analysis methods (i.e. ANOVA, t-tests, Mann-Whitney U-tests) with Bonferroni-correction for multiple comparisons. Exhaled breath composition will be evaluated through a stepwise application of statistical data reduction approaches. Bonferroni-corrected, non-parametric one-way analyses of variance (Kruskal-Wallis tests) will be employed to select significant discriminatory mass-to-charge (*m/z*) peaks. Thereafter, principle component analysis, multivariate analysis of variance and canonical analysis will be used to extract meaningful summary statistics. Data analysis will be done with Matlab (R2016b and newer, The MathWorks Inc., Natick, MA, US) and R (Development Core Team, R Foundation for Statistical Computing, Vienna, Austria) based on data analysis tools developed at ETH Zurich. The SESI-MS data will be acquired and mass calibrated with the Analyst TF 1.7 and PeakView 2.1 software (Applied Biosystems Sciex, Toronto, ON, Canada).

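### The main objective is discriminative capacity, but the breath analysis in 7.3 selects peaks by p-value and derives no classification accuracy from them

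*Protocol*

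**What the plan says.** Section 3.2 sets the aim: "The main objective is to provide evidence for the discriminative capacity of breath analysis by SESI-MS in children with respiratory symptoms", followed by translation of the technique into routine care. The synopsis (Objective(s)) has a nearly identical sentence with a different key word: "The main objective is to provide evidence for the effectiveness of breath anlaysis by SESI-MS in children with respiratory symptoms".

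The hypotheses in 3.2 and 4.1 concern individual children. Two examples are "The development of asthma later in life can be predicted by specific breath prints and/or specific molecules in exhaled breath in preschool children" and "Breath analysis is capable to classify school-aged children with and without asthma". Others are that protracted bacterial bronchitis (PBB) can be diagnosed earlier and that controlled and uncontrolled asthma can be told apart. One research question in 4.1 asks whether preschool breath analysis is diagnostic for PBB.

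The primary outcome (4.2.1) is the molecular composition of breath, with no accuracy measure attached. Section 7.3 fixes the analysis: "Bonferroni-corrected, non-parametric one-way analyses of variance (Kruskal-Wallis tests) will be employed to select significant discriminatory" mass-to-charge peaks. After that, principal components, MANOVA and "canonical analysis will be used to extract meaningful summary statistics".

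Sensitivity and specificity appear only for two earlier studies: 77% and 94% for exhaled nitric oxide (3.1.4.2), and 89% and 95% for a gas-chromatography breath test (3.1.4.4).

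**The concern.** Predicting, classifying and diagnosing all ask how often a child would be assigned correctly. A Kruskal-Wallis p-value asks whether group distributions differ at all, and its size depends on sample size and number of tests as well as on separation. Section 7.3 uses the word discriminatory for peaks that pass the second kind of test, while 3.2 uses discriminative for the first kind of question.

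If the plan is followed as written, a list of significant peaks and a plot of separated variates could be reported as meeting the main objective. A reader would have no figure to set beside the 77%/94% and 89%/95% that the protocol itself cites, although the stated aim is routine clinical use.

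**Working it through.** **The plan's own figures.** The totals reproduce: 3 × 60 = 180 (WP I), 3 × 30 = 90 (WP III), 180 + 90 = 270, and 0.75 × 180 = 135 (WP II). The 55 to 80 range in 7.1 is taken from a cited factor-analysis rule. The protocol gives no alpha, power or effect size, so the range cannot be recomputed, and it says nothing about accuracy.

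**Question.** How accurate must a peak be to pass the screen in 7.3?

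**Inputs from the protocol:** 60 per group in WP I and 30 per group in WP III (section 6); Bonferroni correction (7.3).

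**Assumptions, not protocol figures:** m = 500 to 3,000 peaks tested; family-wise two-sided alpha of 0.05; normal distributions with equal SD; one peak that only just reaches significance; two groups compared. Specificities of 95%, 90% and a balanced cut-off are all shown because the protocol sets none.

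**Steps.**
1. Critical value z at 0.05/m two-sided: 3.891 (m = 500), 4.056 (1,000), 4.305 (3,000).
2. Null standard error of the rank-based AUC, √[(n1+n2+1)/(12·n1·n2)]: √(121/43,200) = 0.0529 for 60 vs 60; √(61/10,800) = 0.0752 for 30 vs 30.
3. Smallest significant AUC = 0.5 + z × SE. At m = 1,000: 0.5 + 4.056 × 0.0529 = 0.715, and 0.5 + 4.056 × 0.0752 = 0.805.
4. Standardised difference d = √2 · Φ⁻¹(AUC). At m = 1,000: 0.80 and 1.21.
5. Share of cases missed at specificity s = 1 − Φ(d − Φ⁻¹(s)); at the balanced cut-off, Φ(−d/2).

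| Single just-significant peak, m = 500 to 3,000 | 60 vs 60 (WP I) | 30 vs 30 (WP III) |
|---|---|---|
| AUC | 0.71–0.73 | 0.79–0.82 |
| Missed at 95% specificity | 78–81% | 63–69% |
| Missed at 90% specificity | 66–70% | 49–55% |
| Missed at balanced cut-off | 33–35% | 26–28% |

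**Check with three groups.** Using the three-group Kruskal-Wallis threshold at m = 1,000, d is 0.72 to 0.83 with 60 per group (79 to 82% missed at 95% specificity) and 1.02 to 1.18 with 30 per group (68 to 73% missed). The exact value depends on how the three groups are spaced. The picture is the same.

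**Combining peaks.** With k independent peaks of equal strength, D = d√k. For WP I at m = 1,000 and 95% specificity: k = 5 gives D = 1.79 and 44% missed; k = 10 gives D = 2.54 and 19% missed. Correlated peaks would gain less.

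**The cited studies on the same scale.** d = Φ⁻¹(sensitivity) + Φ⁻¹(specificity). For 77%/94%, d = 2.29 and AUC is about 0.95. For 89%/95%, d = 2.87 and AUC is about 0.98.

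The same significant screen is therefore compatible with missing most cases or fewer than one in five. The planned output does not say which.

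**The case against.** The best defence is that performance measures are ordinary analysis-plan content, and such a plan may exist. Section 7.3 uses Kruskal-Wallis to select peaks, which is a proper screening role; 7.2 describes the aim as data reduction; 7.3.3 and 7.3.4 leave room for further methods; and the study calls itself an exploratory pilot. Part of this stands: nothing in 7.3 is false, and no decision rule says that a significant screen licenses clinical use. But the protocol did choose its methods and did attach the word discriminatory to a p-value. The open-ended clauses commit to no accuracy measure, and an exploratory study can still report an AUC with its interval.

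Three stronger readings are tempting, and the documents do not support them.
- A reader might infer that the study's test would miss four cases in five. That figure belongs to one just-significant peak in WP I at an assumed 95% specificity. The protocol's object is the whole breathprint (3.1.4.3), and the figure falls to about two in three in WP III, where the classify hypothesis sits, and to about one in three at a balanced cut-off in WP I. Setting it against the cited 89%/95%, which is reported for breath analysis as a whole, would also be uneven.
- A reader might infer that the plan produces nothing beyond tests and components. Canonical analysis does give variates that separate groups; what is absent is a classification result derived from them.
- A reader might take the synopsis word effectiveness as a flaw of design. It is a wording mismatch with 3.2 and needs only to be aligned.

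**Conclusion.** The point holds as a mismatch between the stated question and the stated method. Sections 3.2 and 4.1 ask about discrimination, classification, diagnosis and prediction; 7.3 answers whether groups differ. It should be corrected, but it does not undermine the design or the data collection.

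The size is illustrative and rests on the assumed number of peaks, alpha, normal model and specificity. A peak that just passes the screen could have an AUC near 0.71 to 0.73 in WP I or about 0.8 in WP III, well below the values implied by the two cited studies. A combination of peaks could do much better. The conclusion does not depend on the exact figures: a p-value does not fix accuracy, and the protocol plans no measure that does.

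**What to change.** In 7.3, keep the Bonferroni-corrected Kruskal-Wallis test as a screening step. For each stated contrast, make the main summary the AUC of the combined breathprint, together with sensitivity at a specificity that the sponsor fixes in advance, both with 95% confidence intervals. The contrasts are:
- healthy vs symptomatic;
- high vs low asthma risk;
- healthy vs asthma at school age;
- allergic vs non-allergic asthma;
- asthma vs none at age six;
- PBB, and controlled vs uncontrolled asthma, where the data allow. The protocol plans no PBB group size, enrols controlled asthmatics in WP III (5.1) and expects 10 to 15 children in WP IV (section 6), so these two may support only descriptive figures.

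Obtain the figures by cross-validation with peak selection repeated inside each fold, so that every child is used and selection does not inflate the result. Reserve the words discriminative, classify, diagnostic and predict for claims based on these figures. Align the synopsis objective with 3.2.

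The cost is wording in two places and some extra analysis; no new participants or measurements. The reported figures will look less favourable and the intervals will be wide. For a sensitivity of 77%, the approximate half-width is 1.96 × √(0.77 × 0.23/60) = 11 points with 60 cases and 1.96 × √(0.77 × 0.23/30) = 15 points with 30.
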